5. TREATMENT ALLOCATION AND BLINDING

Treatment Allocation

Procedures for Randomization

Central randomization will be implemented in this study. In the main study, subjects will be randomly assigned to 1 of 3 treatment groups based on a computer-generated randomization schedule prepared before the study by or under the supervision of the sponsor. The randomization will be balanced by using randomly permuted blocks and stratified by region. Similarly, subjects eligible for the late boost vaccination will be randomly (3:1 ratio) assigned to active vaccine or placebo. The randomization will be balanced by using randomly permuted blocks and stratified by region (USA, East Africa: assuming sufficient numbers from Rwanda in the LTE phase) and by group randomized to in the main study (Group 1/Group 2).

The interactive web response system (IWRS) will assign a unique treatment code, which will dictate the treatment assignment and matching study vaccine for the subject. The requestor must use his or her own user identification and personal identification number when contacting the IWRS, and will then give the relevant subject details to uniquely identify the subject.

Blinding

The subjects, study-site personnel (except for those with primary responsibility for study vaccine preparation and dispensing), and investigator will be blinded to study vaccine allocation of the main study until Week 72, with the exception of the partial unblinding for the start of the LTE phase (see below). The sponsor will be blinded to study vaccine allocation until the primary (Week 28) analysis (see Section 11.6).

The pharmacist with primary responsibility for vaccine preparation (see Section 14.3) will not be blinded to the study vaccine. In order to preserve blinding, he/she will place an overlay on the syringes. Administration of study vaccine to the subjects can be performed by a qualified healthcare provider from the study site (including the pharmacist who prepared the study vaccine) who will have, on the day of administration, no other study function related to safety, study data evaluation or recording of AEs for those subjects that he/she vaccinated on that day.

The investigator will not be provided with randomization codes. The codes will be maintained within the IWRS, which has the functionality to allow the investigator to break the blind for an individual subject.

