11.3. Sample Size Determination

The sample size in this study is regarded to be appropriate to assess the safety and tolerability of the different vaccine regimens. Placebo recipients are included for blinding and safety purposes and will provide control specimens for immunogenicity assays. With 25 individuals in a vaccine regimen, the observation of 0 such reactions would be associated with a 95% confidence that the true rate is less than 12%. For Group 2 with Mosaic and Clade C gp140 (n=100), there would be 95% confidence that the true rate is less than 3% when 0 events are observed. The following table shows the probabilities of observing at least one AE given true AE rates.

Probability of Observing at Least One AE in n Subjects

True AE Rate	n = 25	n = 100
0.1%	2%	9.5%
0.5%	12%	39%
1.0%	22%	63%
2.5%	47%	92%
5.0%	72%	99%
10.0%	93%	100%

The primary population for the safety analyses will consist of all subjects who received at least 1 dose (Ad26.Mos4.HIV or placebo).

Anticipating a dropout rate of approximately 10%, the sample sizes will allow detection of approximately 1.85-fold differences in Env-binding Ab titers, generally accepted to be biologically relevant, between the groups with Mosaic and Clade C gp140 (approximately 90 evaluable subjects) and their corresponding group with Clade C gp140 only (approximately 22 evaluable subjects); with 80% probability, assuming a 2-sided 5% Type I error and an SD of 0.4 on the log₁₀ scale.

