## **2.2. Pooling Algorithm for Analysis Centers**

Not planned, subgroups analyses by region are described in section 2.4.

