### 6.3. Immune Response Analysis

No formal hypothesis on immunogenicity will be tested however at post-baseline timepoints the differences between the 2 active groups (Ad26.Mos4.HIV Clade C +Mosaic gp140/ Ad26.Mos.HIV + Clade C gp140) and the differences between the post-baseline timepoint (Week52 vs Week 28) within the same vaccine will be explored by means of a GMR including 95%CI and by a 2-sample t-test on the log data if those are normally distributed or by a Wilcoxon rank sum test otherwise. Those analyses will be performed on the following assays:

- ELISA: Clade C (C97ZA.012), Mos1, Clade B (1990a)
- ADCP: Clade C (C97ZA.012), Mos1, Clade B (1990a)
- ELISpot: Env peptide pool PTE, Gag peptide pool PTE, Pol peptide pool PTE, Env peptide pool Mos1

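### The between-group GMR, confidence interval and test leave out the randomisation strata; if region or main-study group predicts titer, the interval is too wide and the test conservative (minor)

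*SAP*

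**What the plan says.** Allocation: Protocol Section 5 says of the main study that "The randomization will be balanced by using randomly permuted blocks and stratified by region". The 3:1 late-boost allocation uses permuted blocks too, stratified by region (on condition that enough Rwandan participants are in the long-term extension, LTE) "and by group randomized to in the main study".

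Analysis: SAP 6.3 explores the difference between the two active groups at post-baseline visits with a GMR, its 95% CI and a test, "by a 2-sample t-test on the log data if those are normally distributed or by a Wilcoxon rank sum test otherwise". Protocol 11.4 likewise names only unstratified two-sample tests. SAP 6.1 applies the main-study rules to the late boost without writing out a late-boost contrast. On centres and region, SAP 2.2 says "Not planned, subgroups analyses by region are described in section 2.4". Region otherwise appears as a baseline characteristic (SAP 4.1) and as a subgroup for graphs (SAP 2.4 and 6.3). None of these is an adjustment.

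Sample size: Protocol 11.3 claims detection of "approximately 1.85-fold differences in Env-binding Ab titers" "with 80% probability", with "approximately 90 evaluable subjects" in the combined-protein group and about 22 in the Clade C group, "assuming a 2-sided 5% Type I error and an SD of 0.4 on the" log10 scale.

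**The concern.** Stratified blocks balance region between the arms, so a difference between regions largely drops out of the estimated contrast. A two-sample standard error still counts that difference as noise. If region matters for titer, the reported interval is wider than the real sampling error and the test rejects a true null in fewer than 5% of trials.

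Protocol 3.2 cites Week 52 GMRs and intervals (pooled with a sister study) in support of the chosen regimen, so intervals that match the design are worth having. The late boost is smaller (at least 48 subjects, so 36 and 12 at 3:1) and has up to two strata, which leaves less precision to spare.

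**Working it through.** **Inputs from Protocol 11.3:** SD σ = 0.4 on log10, two-sided α = 0.05, n = 90 and 22, target log10(1.85) = 0.267.

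**Assumption:** R² is the share of log10-titer variance explained by the strata. The documents give no figure, so a range of 0 to 0.30 is shown. Total SD is held at 0.4, because the protocol's calculation is an unadjusted one. For two equal-sized regions, R² corresponds to a regional difference of 2 × 0.4 × √R² log10.

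**Step 1, the plan's own figure.**
- SE = 0.4 × √(1/22 + 1/90) = 0.0951.
- Power = Φ(0.267/0.0951 − 1.96) = Φ(0.848) = 80.2%; 79.5% with the t distribution.
- Detectable fold = 10^((1.96 + 0.842) × 0.0951) = 1.85.

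The stated figure reproduces from the unadjusted formula, so the sample size takes no credit for stratification.

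**Step 2, interval width.** Unadjusted half-width = 1.982 × 0.0951 = 0.189 log10, a factor of 1.544 either way. With a region term, the SE is multiplied by √(1 − R²) and one degree of freedom is spent.

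| Assumed R² | Implied regional difference | CI factor, adjusted | Narrower on log scale | Detectable fold, adjusted | Power at 1.85-fold, adjusted (t) |
|---|---|---|---|---|---|
| 0 | none | 1.544 | 0% | 1.85 | 79.5% |
| 0.05 | 0.18 log10 (1.5-fold) | 1.527 | 2.5% | 1.82 | 81.5% |
| 0.10 | 0.25 log10 (1.8-fold) | 1.510 | 5.1% | 1.79 | 83.5% |
| 0.20 | 0.36 log10 (2.3-fold) | 1.475 | 10.5% | 1.73 | 87.5% |
| 0.30 | 0.44 log10 (2.7-fold) | 1.438 | 16.3% | 1.67 | 91.4% |

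**Step 3, error rate of the planned test.** With perfect balance, the unadjusted test rejects a true null with probability of about 2 × (1 − Φ(1.982/√(1 − R²))). That is 3.7% at R² = 0.10 and 1.8% at 0.30. A simulation used stratified permuted blocks at 1:4, 25 and 100 randomised, 10% dropout, and two regions split 50/50 or 70/30 (both assumed). It gave:
- R² = 0: mean SE 0.094 against a true SD of 0.095; type I error 5.0–5.3%.
- R² = 0.10: mean SE 0.094 against 0.091; coverage about 96%; type I error 3.9–4.3%.
- R² = 0.30: mean SE 0.094–0.095 against 0.081–0.082; coverage about 98%; type I error 2.1–2.4%.

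The region-adjusted model kept type I error at 4.9–5.2% throughout. Simulated power at 1.85-fold, unadjusted against adjusted, was 80.5% and 80.5% at R² = 0, 80.6% and 83.3% at 0.10, and 83.1% and 91.7% at 0.30.

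**Step 4, late boost, active versus placebo (36 vs 12; SD 0.4 assumed to carry over).** SE = 0.4 × √(1/36 + 1/12) = 0.133. The unadjusted CI factor is 1.855. With two stratum terms it is 1.857 at R² = 0, 1.80 at 0.10 and 1.68 at 0.30. If the strata explain nothing, the two extra terms cost almost nothing.

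**The case against.** The strongest reply is that these comparisons are exploratory, that no formal hypothesis is tested (SAP 1.3 and 6.3, Protocol 11.4), and that the possible error is on the safe side. That stands, and it keeps the point minor. Four stronger readings are tempting and should be resisted.

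- **That the intervals are certainly too wide.** This needs a stratum that predicts titer. Stratifying by region, and naming it as a subgroup, shows only that the sponsor thought region might matter.
- **That power is lost or the sample size undermined.** Step 1 shows that the 1.85-fold claim rests on an unadjusted calculation, and the unadjusted analysis delivers it. What is forgone is extra precision.
- **That the conclusion on breadth is affected.** The GMRs listed in SAP 6.3 measure magnitude on single antigens or peptide pools. Breadth is judged by the number of clades (Protocol 11.4) and by magnitude-breadth curves.
- **That the t-test inflates type I error because the groups are so unequal in size.** A pooled-variance test would do so under some assumed SDs: about 11% with 0.5 in Group 1 and 0.35 in Group 2, but about 1.4% with 0.3 and 0.45. Welch's test stays near 5% in both cases. The SAP does not say pooled, Welch's test is also a two-sample t-test, and the documents give no separate SDs. What remains is an ambiguity worth settling in the same edit.

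Timing is a fair objection too. SAP Section 1 says that outputs up to Week 72 will not be repeated, and the sponsor was unblinded from the Week 28 analysis. Changing the main-study model now would be a post hoc change.

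**Conclusion.** The point holds conditionally and is minor. The planned GMR interval and test ignore the factors used to randomise. If a stratum predicts titer, the interval is too wide and the test conservative, by the amounts in the table; R² of 0.05 to 0.10 means 2.5 to 5%. The GMR point estimate is essentially unaffected, because allocation is balanced within strata, although dropout and the per-protocol set make that balance approximate.

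The size rests on an assumed R², on the protocol's SD of 0.4, and on main-study numbers; the documents do not give group sizes for the LTE. Main-study group can serve as a stratum only when boost active is compared with placebo. In the Group 2 versus Group 1 contrast it is the factor being compared. A reader might infer that the Week 28 to Week 72 comparisons must be redone. The documents do not support that, and the benefit lies mainly in the LTE and late-boost analyses.

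**What to change.** In SAP 6.3, for analyses not yet run, take the GMR, 95% CI and p-value from a linear model on log10 values:

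- Group 2 versus Group 1 during the LTE: regimen and region.
- Late boost, active versus placebo: boost arm, main-study group and, if it was used as a stratum, region. Write this contrast out, since the SAP only implies it.
- Late boost, Group 1 versus Group 2: main-study group as the compared factor, plus region.

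State that unequal-variance or robust standard errors are used, given the 4:1 group sizes. Name the van Elteren test, with the same strata, as the rank-based alternative. Label any region-adjusted re-analysis of results up to Week 72 as a sensitivity analysis.

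The cost is a few sentences in the SAP, a few lines of code and one or two degrees of freedom. No new data are needed.

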#### Humoral response

For all the humoral assays the immune response values will be  $\log_{10}$ -transformed before any further handling. The  $\log_{10}$ -transformed values will be used throughout the analysis. In the graphs, original values will be displayed on the  $\log_{10}$  scale.

For each assay and at each time point geometric mean of actual values, geometric mean increases and percentage of responders, all with corresponding 95% CIs will be provided by group in the tables. Within each group, the mean fold change of Week 52 to Week 72 will be reported. The definition of responders is defined in section 6.4. for each assay. Graphical presentations will be provided displaying dots for the subject values and including the geometric mean and the percentage of responders. If available, baseline values will be summarized pooling all the groups and will be displayed on the left of each graph. Data from post-baseline timepoints will be plotted next to each other for each group, a symbol will identify the geometric mean (or the median) of each group and timepoint.

In the graphs the actual values will be shown and the LLOQ cut-off will be visualized, the values below LLOQ or below LOD will be visualized with the value imputed as described in section 6.3.

Graphs by subgroups listed in section 2.4 will be done for ELISA (Clade C C97ZA.012, Mos1) and for ADCP (Clade C C97ZA.012), Mos1).

Durability will be displayed as a line plot showing the GM/median for each vaccine regimen.

Magnitude-breadth (MB) plot for the ELISA assay will be provided at post-baseline timepoints to explore the magnitude and breadth of each individual serum sample assayed (antibody titers of 5 Clades). MB curves will show, for each possible titer threshold, the proportion of antibody titers greater than this threshold. The group-specific curve obtained as the average MB across all subjects in that group will be displayed. The AUC-MB is calculated as the average of the titers over the panel of antigens.

For BAMA the median will be reported instead of the geometric mean. Cumulative number of responses across the IgG/antigen classes will be tabulated.

Magnitude-breadth (MB) plots for the BAMA assay will be provided at post-baseline timepoints to explore the magnitude (MFI of IgG3 and of IgG breadth binding antibodies) and breadth of each individual serum sample assayed. MB curves will show, for each possible MFI threshold, the fraction of antigens with MFI greater than this threshold. The group-specific curve obtained as the average MB across all subjects in that group will be displayed. The AUC-MB is calculated as the average of the MFI over the panel of antigens.

Scatter plots of individual mean magnitudes and breadth per category (IgG-t gp120, IgG-t gp140, etc.) will be provided as well.

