• To explore T-cell and Ab epitope mapping.	• Epitope mapping of Ab to Env and T-cell responses to Gag/Pol/Env (PTE and vaccine peptide pools).
To explore gene expression patterns using PBMCs.	 Regulation of genes (or clusters) that predict specific immune responses and human leukocyte antigen (HLA) typing.
To explore B-cell responses.	Ab-producing B-cells and characterization of B-cell memory development.
To explore immune responses against the viral vector.	Ad26 nAbs (titer).

^d The follicular helper T-cells and memory differentiation was included as secondary objective for the main study. Due to difficulty qualifying the assay for these specific markers, these T-cell responses will be considered as an exploratory objective for the late boost vaccination.

	Objectives		Endpoints	
•	To explore the social impact of participation in an HIV-vaccine study for subjects via a social impact questionnaire.	•	Social impact.	
•	To explore durability of the immune responses to the vaccine regimens in the groups selected for the Long-term Extension (LTE) phase.	•	Available samples from time points during the LTE phase will be used for determination of long-term durability of the immune responses.	

In addition, following exploratory objectives are applicable to the late boost vaccination only:

	Objectives		Endpoints		
•	To assess Env-binding antibody Ab responses following late boost vaccination approximately 3 years after receiving the 4 th vaccination of the primary vaccination series.	•	Env-specific binding Abs [ELISA] at 3, 7 or 14 ^e days and 28 days post late boost vaccination (titers and breadth).		
•	To explore the role of Ad26 neutralizing antibodies on the immune response to a late boost vaccination.	•	Ad26 neutralizing antibodies at the time of vaccination relative to the immune response as evaluated by ELISA.		
•	To compare the immune response to late boost vaccination with a vaccine matched to the primary vaccination series (Group 2) vs a closely related vaccine (Group 1).	•	Relative ELISA magnitudes between groups randomized to Group 1 vs Group 2 in the main study.		
•	To evaluate whether humoral responses induced by a late boost vaccination are able to mediate protection in non-clinical passive transfer studies.	•	Analysis of protection against HIV-related challenge viruses, such as simian human immunodeficiency virus (SHIV), in a suitable animal model, and/or in vitro.		

See Section 9 for evaluations related to endpoints.

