4.4. Inclusion and Exclusion Criteria for the Long-term Extension Phase

Each potential subject must satisfy all of the following inclusion criteria to be enrolled in the LTE phase of the study upon completion of the final main study visit at Week 72.

- 1. Each subject must sign an ICF appendix for the LTE phase indicating that he or she understands the purpose of and procedures required for the LTE phase and is voluntarily willing to participate in the LTE phase of the study.
- 2. Subject must be randomized to Group 1 or Group 2 of the main study.
 - Note: Upon sponsor unblinding at the Week 28 analysis, subjects randomized to Group 1 or Group 2 who have received all 4 vaccinations, will be asked to participate in the LTE phase and sign the ICF appendix for the LTE phase at Week 72. Subjects who attend their Week 72 visit prior to the sponsor's unblinding at the Week 28 analysis, will be enrolled in the LTE phase if they consent and sign the ICF appendix for the LTE phase and meet the eligibility criteria for the LTE phase. When the Week 28 sponsor unblinding subsequently occurs, subjects that started the LTE phase but turn out to have received placebo in the main study will be withdrawn from the LTE phase.
- 3. Subject must have received all 4 vaccinations of the main study.
- 4. Subject must be negative for HIV infection at the final main study visit at Week 72.
- 5. Subject must be willing/able to adhere to the prohibitions and restrictions for the LTE phase, as specified in the protocol and study procedures.

Any potential subject who meets any of the following exclusion criteria at the end of the main study will be excluded from participating in the LTE phase of the study.

- 1. Subject has any condition for which, in the opinion of the investigator, participation would not be in the best interest of the subject (eg, compromise the well-being) or that could prevent, limit, or confound the protocol-specified assessments.
- 2. Subject is planning to participate in an interventional study during the LTE phase, concerning studies with investigational HIV vaccines or other investigational HIV prevention which could be determined to interfere with HIV vaccine response in this study (ie, CD4-Ig depleting Env-specific Abs), which are disallowed.

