### **2.3.2. Per-Protocol Immunogenicity Analysis Set**

The per protocol immunogenicity (PPI) population consists of all subjects who have received at least the first three vaccinations, according to the protocol-specified vaccination schedule (+/- 2 weeks), have at least one measured post-dose blood sample collected and were not diagnosed with HIV during the study. Samples taken after Week 48 from subjects in the PPI population who missed the 4th vaccination or did not receive the 4th vaccination in the protocol-specified time window (+/- 2 weeks) will be excluded from the analysis.

The analysis of the immune responses will be performed on the per protocol immunogenicity population.

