**6.4. Handling of Missing and/or Invalid Immune Response Data**

Analysis will be carried out on the available data, no imputation will be done for missing samples. BAMA and ICS unreliable values should be excluded from the analysis: those records will be flagged in the SDTM dataset.

LLOQs by assay/test are listed in section 6.5. Values below LLOQ or LOD will be handled as follows:

- Calculation of Geomean (humoral response except ADCP) and median (cellular response):
  - o values < LLOQ are imputed =LLOQ/2
  - o values = LOD are imputed =LLOQ/2

For ADCP only:

- o values < LOD are imputed =LOD/2

- Calculation of fold increases from baseline:
  - o values <LLOQ are imputed =LLOQ
  - o values =LLOQ are imputed = LLOQ

For ADCP only:

- o values < LOD are imputed =LOD

Values above the upper limit of quantification (ULOQ) will be handled as follows:

- Calculation of geomean and median:
  - o Values>ULOQ are imputed=ULOQ.
- Calculation of fold increases from baseline:
  - o Values >ULOQ are imputed with ULOQ

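### Durability is planned only as a line of group means on whoever has a sample, with no within-subject change after Week 72, so a change in who is sampled can show as a change in antibody level

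*SAP*

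**What the plan says.** The exploratory objective in Protocol 2.1 is "To explore durability of the immune responses to the vaccine regimens in the groups selected for the Long-term Extension (LTE) phase", and its endpoint relies on whatever LTE samples are available. LTE visits fall at Weeks 96, 120, 144, 168, 192 and 216.

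In the SAP:

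- **Display (6.3, Humoral response).** "Durability will be displayed as a line plot showing the GM/median for each vaccine regimen". No time span, subject set or n per visit is given for this plot.
- **Latest change between visits (6.3).** "Within each group, the mean fold change of Week 52 to Week 72 will be reported".
- **Other time contrast (6.3).** The plan explores "the differences between the post-baseline timepoint (Week52 vs Week 28) within the same vaccine", using a GMR and a 2-sample t-test or rank sum test. Nothing comparable is listed for any LTE visit.
- **Tables (6.3).** "For each assay and at each time point geometric mean of actual values, geometric mean increases and percentage of responders" are given with 95% CIs. The fold increases defined in SAP 6.4 are from baseline.
- **Missing samples (6.4).** "Analysis will be carried out on the available data, no imputation will be done for missing samples".
- **Population (2.3.2).** "The analysis of the immune responses will be performed on the per protocol immunogenicity population". This per-protocol immunogenicity (PPI) set requires the first three doses on schedule and excludes subjects diagnosed with HIV. Samples after Week 48 are dropped where dose 4 was missed or out of window.

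Entry to the LTE (Protocol 4.4) needs a signed consent appendix, a negative HIV status at Week 72 and passing the exclusions, one of which is the investigator's judgement. It also requires this: "Subject must have received all 4 vaccinations of the main study".

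**The concern.** A line of group means shows decay only if the people behind each point are the same, or if those who leave resemble those who stay. Here the contributing group can change between Week 72 and Week 96, when a further consent is needed, and at every later visit as subjects are lost. A step at Week 96 or a late flattening could then be kinetics, a change of cohort, or both, and the planned outputs cannot separate them.

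The other outputs do not close the gap. The geometric mean increase is measured from baseline, and a baseline below the LLOQ is set to the LLOQ. For a subject with such a baseline, the increase is the current titer divided by a constant, so it carries the same composition effect as the geometric mean. The humoral text does not list n among the tabulated statistics, although the ELISpot text does, so a reader may not see the cohort shrink.

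What is at stake is the purpose of the LTE, which Protocol 1.3 says was introduced to assess durability. The two regimen lines will also be compared by eye, although Group 1 is much smaller than Group 2.

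**Working it through.** **Inputs from the documents (Protocol 11.3).** SD 0.4 on the log10 scale; about 22 evaluable in Group 1 and about 90 in Group 2. These are planned evaluable numbers, not LTE counts.

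**Assumptions, because the documents give no figure.** Uptake f (share of Week 72 subjects who join the LTE), the difference d in mean log10 titer between joiners and non-joiners, and the correlation rho between visits.

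**1. The plan's own figure.** Detectable difference = (1.960 + 0.842) x 0.4 x sqrt(1/22 + 1/90) = 0.2665 log10, or 1.85-fold. It reproduces, so the SD and group sizes are usable here.

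**2. False step if joining is related to titer.** With no true decay, the expected step when the line passes from all Week 72 subjects to joiners is (1 - f) x d.

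- f = 0.8, d = 0.1: 0.2 x 0.1 = 0.02 log10, or 1.05-fold.
- f = 0.6, d = 0.3: 0.4 x 0.3 = 0.12 log10, or 1.32-fold.

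The step goes down by the same factor if joiners have the lower titers. Over a wider range, f = 0.5-0.9 and d = 0.1-0.4 log10 (0.25 to 1 SD), it runs from 1.02- to 1.58-fold.

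**3. False step by chance, if joining is unrelated to titer.** With m of n subjects continuing, SE = 0.4 x sqrt(1/m - 1/n). The 95% limit on the fold scale is 10^(1.96 x SE).

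| Uptake | Group 1 (n = 22) | Group 2 (n = 90) |
|---|---|---|
| 60% | m = 13, 1.38-fold | m = 54, 1.17-fold |
| 70% | m = 15, 1.30-fold | m = 63, 1.13-fold |
| 80% | m = 18, 1.20-fold | m = 72, 1.10-fold |

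**4. Does pairing remove it?** A simulation used no true decay, joiners 0.2 log10 (0.5 SD) higher and rho = 0.8. The available-sample step was 1.16-fold for 22 to 15 subjects and 1.15-fold for 90 to 63. With joiners 0.2 log10 lower, it was 0.86 for 22 to 15. The within-subject fold change was 1.00 in each case.

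**5. Precision of the paired estimate.** The 95% half-width is 10^(1.96 x 0.4 x sqrt(2(1 - rho)/m)). For rho = 0.5 to 0.9 it is 1.59- to 1.23-fold with m = 15, and 1.26- to 1.11-fold with m = 63. Treating the two visits as independent samples (rho = 0) gives 10^(1.96 x 0.4 x sqrt(2/15)) = 1.93-fold and 10^(1.96 x 0.4 x sqrt(2/63)) = 1.38-fold.

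**The case against.** The strongest reply has four parts.

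- **The display is exploratory and follows the protocol.** No hypothesis is tested, and the endpoint itself refers to available samples. This stands, and it limits the weight of the point. It does not supply a decay estimate.
- **Further analyses are allowed.** Protocol 11.6 permits additional LTE analyses, and SAP 6.3 permits additional timepoints analysed by its stated approaches. This is permission, not a plan. The stated approach for a time contrast within one vaccine is a 2-sample test, which ignores pairing.
- **Selection on titer has no direct route.** Subjects entering the LTE are not told which active group they were in (Protocol 5), and exploratory immunogenicity results are not returned to subjects or investigators (Protocol 16.2.4). This is a fair reason to expect a small systematic step. Indirect links, for example through region, remain possible, and the chance step in the small group needs no selection.
- **The line may not cross Week 72.** The SAP introduction says outputs up to Week 72 will not be repeated, so the line could start later. It would then have no Week 52 or Week 72 anchor, and the missing change from those visits would matter more.

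A reader might also infer that every main-study subject feeds the line up to Week 72, and that the four-dose entry rule creates the break at Week 96. The documents do not support this. The set is PPI, HIV-diagnosed subjects are already out, and samples after Week 48 already require an on-time dose 4. What changes after Week 72 is consent, the LTE exclusions and retention.

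**Conclusion.** The point holds as a gap in the analysis plan that is cheap to close. The SAP plans no within-subject change beyond Week 52 to Week 72, and its durability line uses available PPI samples with no stated span or common-subject rule. If the line spans Week 72, composition can appear as kinetics.

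It would go too far to conclude that the line will be biased or in which direction. Uptake, the joiner difference and the correlation are assumptions. The 1.05- to 1.32-fold range depends on 60-80% uptake and a 0.1-0.3 log10 difference; with high uptake or consent unrelated to titer, the systematic part is negligible. Chance can still move Group 1 by up to 1.30-fold at 70% uptake, against 1.13-fold in Group 2. These steps are below the 1.85-fold design difference. They are not trivial beside the Mos1 ratio of 1.4 (95% CI 1.1-1.9) that Protocol 3.2 cites in favour of the bivalent regimen. The need for a paired estimate does not depend on these assumptions.

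**What to change.** Add to SAP 6.3, by regimen:

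1. Paired geometric mean ratios with 95% CI of each LTE visit to Week 52 and to Week 72, in PPI subjects with both samples, using only samples taken before any late boost.
2. A durability line, or a second line, for LTE participants carried back to their own Week 52 and Week 72 values, with the time span stated and n printed at each visit.

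The cost is SAP wording and some programming on data already collected. The Week 52 and Week 72 values must be re-run for LTE participants, as an exception to the rule that outputs up to Week 72 are not repeated. The part of this plot before Week 72 has fewer subjects. Limiting to samples before the late boost also means that the Week 216 ratio rests on subjects outside the late boost extension, which is another reason to print n.

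Pairing removes differences in level between those who stay and those who leave. It does not remove bias if the two groups decay at different rates, and the text should say so.
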